The project aims to create therapy groups for children to improve their mental and emotional wellbeing. Each therapy group runs for one hour after school for six weeks, one half an hour focussing on physical activity (led by a local sports club) and another half an hour focusing on psychoeducation, led by NHS staff (e.g mental health nurse, psychiatrist, psychologist, Psychological Well-being Practitioners). The physical health aspect of the groups encompasses a broad range of physical activities, adapted to try at home. The groups also enable young people to learn about how and why anxiety and depression occur, and how we can learn ways of managing them.

This project is especially crucial given the nature of the COVID-19 pandemic, and ensuring the safety of staff and patients, by allowing the delivery of the interventions over video-conferencing software.

3. Objectives and Hypotheses

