3.3. Hypotheses

- A) Exposure to the intervention will be associated with significantly lower mean score of depression and anxiety by comparison to a waitlist (delayed intervention) control group
- **B)** After the control group is exposed to the intervention, there will be no significant differences in mean depression and anxiety level between the two groups (immediate intervention group, delayed intervention group)
- C) Mean depression and anxiety severity for all participants at the end of the 6-month follow-up period will be significantly lower than baseline severity (prior to intervention), but not significantly different to end-of-treatment severity, indicating maintenance of gains
- **D)** Attitude towards physical exercise will significantly improve following the intervention, and be maintained at the 6-month follow-up period.

4. Study design

This will be a pragmatic, stepped wedge, open-label, randomised controlled trial. Consenting participants will be randomly assigned to two groups, by a research assistant using a computerized randomization algorithm (applying a simple 1:1 randomization schedule). Participants will take part in one of the two 6-week interventions, depending on their group assignment. They will complete an online survey with standardised measures at baseline (prior to starting the interventions), after 6 weeks (after group 1 has finished and prior to group 2 commencing), after 12 weeks (post-treatment) and finally after 6 months (follow-up). All measures will be completed online using an industry-standard survey system which automatically sends email reminders to consenting participants.

The interventions will be delivered using an online approach; weekly online video-conference sessions involving half an hour of psychoeducation and half an hour of physical activity. Both interventions will involve a total of six 1-hour sessions delivered once per week using video-conferencing software that can involve large groups of participants. The study will be carried out in four phases, which are illustrated in Figure 1.

[figure not shown]

Figure 1. Trial design and measurement time-points

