- For those participants aged 16-18 they can provide their own consent if they are deemed to have mental capacity. An information sheet will be provided for their parents to ensure they are aware of participation and what is required.
- Consenting participants will be randomly allocated to the online intervention groups, within their regional area. Allocation will be carried out by a researcher who is independent of the research team, using a computerized randomization schedule. Randomisation will be communicated directly to study participants via email within one week of receipt of their electronic consent form.
- The consent and demographic questionnaires will ask for the participants personal email address. This is to ensure we are able to contact the participants throughout the study period (e.g., sending email reminders). Once they have completed the consent form we will email the participants a unique participant pseudonyms, which cannot personally identify any of the study participants. The participant will then use this pseudonym to identify themselves throughout the rest of the study (i.e., to log in to the online session to ensure anonymity is protected when completing the sessions, and as their identifier when they complete the rest of the measures throughout the study). The Grounded Research team will keep a record of the participants email address and associated pseudonym, so if the participant forgets their code they can contact us. The participants email address will then be deleted when the study has completed.
- The measures will be collected by the research team using a secure, web-based, industry-standard data collection system. Therefore, all data collection will be in electronic form, using unique participant pseudonyms, which cannot personally identify any of the study participants. Participants will receive email reminders (sent confidentially by the research team) at the relevant measurement points (see Figure 1) prompting them to access the survey via the Qualtrics.
- Consenting participants will be made aware that this is not a CAMHS referral, and if CAMHS input is required they will need to access the support through the usual route.

Organisation of the online intervention workshops

- Participants will access one of the two interventions described above; using NHS-approved video conferencing software.
- The sessions will be held after school hours.

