5.1. Sample size calculation

A sample size calculation was performed using the method described by Cohen (1992). There is no precedent for this type of trial in this setting, so it is not known whether exposure to the Home Goals intervention may be associated with small, moderate or large effects on measures of depression, anxiety and physical activity. We have therefore followed conventional sample size calculation methods described by Cohen (1992), expecting a moderate effect size as a conservative assumption. In order to detect a moderate effect size using between-groups ANOVA, with 80% power, and an alpha level of 0.05, we estimate that at least 67 participants are needed per group. This would yield a sample size of 134. Expecting a 30% dropout rate, which is common in studies of psychological interventions, we would need to inflate the recruitment target to 192. If we recruit more than the 192, we will accept the young people onto the trial, but we will not collect or analyse their data.

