5.2. Primary analysis

Trial data will be summarised using a CONSORT diagram and all analyses will be based on *intention-to-treat* principles. Missing data will be imputed using an expectation-maximization algorithm (Schafer & Olsden, 1998), prior to conducting formal analyses.

The primary hypothesis test (A) will be based on comparing mean outcome measures between groups at week 8, as shown in Figure 1. Mean PHQ-A scores will be compared between groups using analysis of covariance (ANCOVA), controlling for baseline severity.

Sensitivity analyses will be performed to assess the robustness of the main findings. This will involve repeating the above analysis including a random intercept for each trial site and additionally introducing "role" as a covariate (admin; mental health; other clinical role) and any other baseline demographics that may be unbalanced between groups.

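### The primary ANCOVA and the 67-per-group calculation treat participants as independent, although at the 6-week comparison group 1 alone has been treated in shared online therapy groups

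*Protocol*

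**What the plan says.** **Delivery.** Section 2 of the protocol says "The project aims to create therapy groups for children to improve their mental and emotional wellbeing", each running weekly for six weeks under NHS staff and a local sports club. Section 4 describes video-conference sessions that can take large numbers. No group size is given.

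**Timing.** Section 4 places the 6-week survey after group 1 has finished and before group 2 begins. The synopsis and 5.3 also use week 6. Section 5.2 places the primary test at week 8.

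**Allocation.** Section 4 describes individual randomisation, "applying a simple 1:1 randomization schedule". Section 4.4 says "Consenting participants will be randomly allocated to the online intervention groups, within their regional area".

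**Primary model (5.2).** "Mean PHQ-A scores will be compared between groups using analysis of covariance (ANCOVA), controlling for baseline severity". A sensitivity analysis will involve "repeating the above analysis including a random intercept for each trial site".

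**Sample size (5.1).** The calculation is for a moderate effect by between-groups ANOVA, "with 80% power, and an alpha level of 0.05, we estimate that at least 67 participants are needed per group". That gives 134 analysed and 192 recruited at 30% dropout. Data from anyone beyond 192 will not be collected or analysed.

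**The concern.** Young people in one online group share leaders, coaches, peers and session quality, so their later scores may be correlated. At the 6-week comparison this can arise only in group 1, because group 2 has had no sessions. The design is then partially nested: one arm is made up of clusters and the other of independent individuals. ANCOVA with baseline as its only covariate treats all 134 as independent. If the correlation is real, the standard error of the treatment effect is too small, the nominal 5% test rejects too often, and the 80% power was not worked out for this design.

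The planned sensitivity analysis does not cover the gap. A site intercept shared by both arms describes differences between sites that affect treated and untreated alike. It does not describe variation present only among the treated. The robustness check could therefore repeat the error and seem to confirm the result.

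**Working it through.** **1. The plan's own figure.** Inputs from 5.1: alpha 0.05 (two-sided assumed), power 80%, moderate effect (read as d = 0.5, f = 0.25). Two-group ANOVA gives 64 per group. The stated 67 gives 81.9% power, so it errs on the safe side, and 134/0.7 = 191.4, i.e. 192, reproduces. No clustering allowance is visible, and the small gap between 64 and 67 is not part of this point.

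**2. Type I error of the stated model.** Let m be the number per online group in group 1 (assumed). Only group 1 carries the design effect DE = 1 + (m − 1) × ICC, so the true variance over the nominal is (DE + 1)/2, and type I error = 2 × [1 − Φ(1.96/√ratio)].

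| m | ICC | DE | Ratio | Type I error |
|---|---|---|---|---|
| 8 | 0.01 | 1.07 | 1.035 | 5.4% |
| 12 | 0.02 | 1.22 | 1.11 | 6.3% |
| 8 | 0.05 | 1.35 | 1.175 | 7.1% |
| 17 | 0.05 | 1.80 | 1.40 | 9.8% |

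The value 17 is 67 divided over the four localities named in 4.1.

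Simulating the stated ANCOVA (67 per arm, baseline correlation 0.5, 20,000 runs) gave 4.9% with no clustering and, at ICC 0.05, 7.3% with 8 groups and 10.1% with 4 groups.

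**3. Effect of the site intercept.** In 4,000 simulated runs with one delivery group per site and ICC 0.05, the stated ANCOVA and the same model with a site intercept gave 10.2% and 10.4% (4 groups), and 7.1% and 7.3% (8 groups). The intercept corrects nothing.

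**4. Power of a test with the right variance.** Assume ICC 0.05, d = 0.5, 67 per arm and k = 67/m groups. Write V1 and V2 for the arm variances times 67.
- Unadjusted: V1 = DE, V2 = 1.
- Adjusted at r = 0.5, ICC on total variance: V1 = m × 0.05 + (1 − 0.05 − 0.25), V2 = 0.75.
- Satterthwaite df = (V1 + V2)² / [V1²/(k − 1) + V2²/66].
- Non-centrality = 0.5/√[(V1 + V2)/67]; power is from the non-central t distribution.

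| m | r | V1 | V2 | df | Non-centrality | Power |
|---|---|---|---|---|---|---|
| 8 | 0 | 1.35 | 1 | 21.1 | 2.67 | 72% |
| 17 | 0 | 1.80 | 1 | 7.0 | 2.45 | 56% |
| 8 | 0.5 | 1.10 | 0.75 | 19.8 | 3.01 | 82% |
| 17 | 0.5 | 1.55 | 0.75 | 6.4 | 2.70 | 63% |

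A normal approximation would give 69% in place of 56% for 17 per group unadjusted. It is too optimistic with about four groups.

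**5. Region.** Leaving out region, with allocation balanced within region and no delivery clustering, gave simulated type I error of 4.6% and 4.1% at region variance 0.05 and 0.10 (within-region variance 1).

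**The case against.** **The inflation is conditional.** Participants are randomised individually. If the programme changes nobody's score, membership of a group adds no one-arm correlation and the plain test keeps about 5%. Inflation needs group-specific effects that average to zero. This stands as a limit on the claim. The documents also leave a low ICC plausible, since participants log in under pseudonyms and the sessions are short and structured. A reader might infer that the false-positive rate is certainly too high, but without an ICC or group size the documents do not show that.

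**Power may still be adequate.** The calculation is for ANOVA but the analysis is ANCOVA, and baseline adjustment gives precision that 5.1 did not count. With 8 per group at ICC 0.05 and r = 0.5, power is about 82%. So the documents do not establish that the trial is underpowered. They establish only that the stated power takes no account of clustering.

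**Region.** A reader might infer that omitting region also inflates the error rate. It works the other way: the test becomes slightly conservative and some precision is lost. Nor is it settled that region is a stratum. Section 4.4 may mean only that delivery groups are regional.

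**The time-point.** Section 5.2 says week 8. On section 4's schedule group 2 would by then have started its own groups, and a random effect in group 1 only would be wrong. Week 6 is the likelier reading, as three other places use it, but the remedy depends on it.

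**A separate analysis plan might handle this.** It might, but 5.2 already fixes the primary model and 5.1 the power basis, so both need changing where they stand.

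**Conclusion.** The point holds for the delivery groups. The primary ANCOVA and the 67 per group assume independence that one-arm group delivery puts in doubt, and the site-intercept sensitivity analysis does not correct it. The size depends on values the documents do not give. It is minor with small groups and an ICC near 0.01. It is material with about four groups and ICC 0.05, where type I error roughly doubles and power falls well below 80% even after baseline adjustment. The power figures also assume 67 analysed per arm and an effect of 0.5 SD. Because data beyond 192 participants are excluded, over-recruitment cannot make up a shortfall. This should be changed before analysis; it does not by itself invalidate the trial.

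**What to change.** 1. Reconcile week 8 in 5.2 with week 6 in the synopsis, section 4 and 5.3. The model below is right only if the comparison precedes the start of group 2.
2. Record each participant's online therapy group as it is assigned. Without it the model may be impossible to fit later.
3. In 5.2, make the primary model an ANCOVA with arm and baseline PHQ-A, a random effect for delivery group in group 1 only, arm-specific residual variances, and Satterthwaite or Kenward-Roger degrees of freedom.
4. In 5.1, restate power for an assumed ICC and group size, over a range, without raising enrolment.
5. Reconcile simple randomisation (section 4) with allocation within regional area (4.4). Add region as a fixed effect, for precision, only if allocation is by region and there is more than one delivery group per region. With one per region, the group effect cannot be told apart from a region-by-arm interaction.

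The cost is protocol wording and one recorded identifier. The downside is wider intervals and a lower stated power, which can be substantial if there are only a few delivery groups.

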4.1. Setting and participants

This study will involve adolescents aged 11-18 years old who are on a waiting list for CAMHS services, or have been highlighted by School Champions and School nurses, and are adolescents who would potentially benefit from some low level psychological intervention. The participants will live in the areas covered by RDaSH. Suitable participants should require low level intervention for support in;

understanding their emotions, coping with low mood, anxiety or stress, and learning strategies for improving their overall mental health and wellbeing.

Inclusion criteria

- Any child aged 11-17 (we will accept participants who turn 18 in the trial period) who may benefit.
- Children must attend a school within the Rotherham, Doncaster, North Lincolnshire or Bradford locality

Exclusion criteria

- Adolescents who are already in receipt of psychological therapy
- Adolescents with a diagnosed condition (such as Autism Spectrum Disorder, learning disabilities, severe depression)
- Adolescents experiencing suicidal ideation
- Adolescents with no access to electronic devices
- Anyone who has participated in either Home Goals or Safety Nets before
- Anyone who is 18 at the time of recruiting (we will accept if they turn 18 over the trial period but not before the trial starts)

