4.3. Measures

Primary outcome measure

The PHQ-A is a nine-item questionnaire; each answered on a 0 to 3 Likert scale. Items cover different aspects of depression and are worded negatively. Item scores are summed to produce a total score (range: 0 to 27), where higher scores indicate greater levels of depression. Psychometric testing has indicated that this measure was valid, reliable and acceptable measure of depression in adolescent respondents (Johnson, Harris, Spitzer & Williams, 2002). Diagnostic, criterion and construct validity were found to be adequate.

Secondary measures

- Participants will be asked to provide some demographic information, including age, gender, ethnicity
- GAD-A
- Questions related to the participants level of activity pre and post-intervention.

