5.3. Secondary analyses

ANCOVA (and sensitivity analyses) described above will be repeated at each of the time-points illustrated in Figure 1 (weeks 0, 6, 12, 36), using the PHQ-A, and using the GAD-A as an outcome, controlling for baseline scores. Outcomes at 6-months follow-up (pooled for both groups) will be compared to outcomes at the baseline assessment, using paired-samples t-tests (or an appropriate non-parametric test depending on the distribution of the data).

These analyses will be repeated at each of the post-intervention time-points illustrated in Figure 1 (weeks 6, 36), using the WEMWBS sub-domain scores. These between and within-group comparisons will also be summarised using effect sizes (Cohen's d).

Post-intervention measures (weeks 6, 36) will be compared to baseline measures (week 0) within each group, using paired-samples t-tests or an appropriate non-parametric test depending on the distribution of the data. Within-sample pre-post treatment effect sizes will also be computed using the method proposed by Minami et al. (2008).

We will carry out an exploratory analysis of knowledge and levels of activity before and after the intervention.

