5.4. Exploratory analyses of mechanisms of change

Change scores will be computed denoting changes in theoretical mechanisms measured using the questionnaires listed in pg. 7. These change scores will be computed between time-point 0 and time-points 6, and 12, denoting changes within the intervention phase.

Residualized change scores across multiple theoretical mechanisms will be entered into a Bayesian network analysis carried out separately for each intervention group, using the post-treatment (weeks 6, 12) PHQ-A as the dependent variable. Each Bayesian network will be trained using a Tree-Augmented Naïve Bayes (TAN) algorithm with adjustment for small cell counts (Friedman, Geiger, & Goldszmidt, 1997). This method offers a data-driven way to model a network of relationships (called attribute dependencies) between predictors and their joint influence over a target outcome (post-

treatment OLBI). TAN produces a simple and parsimonious network model where each predictor is allowed to depend on one additional predictor, thus modelling multiple two-way interactions. Variable selection will be performed using a 10-fold cross-validation procedure (Rodriguez, Perez, & Lozano, 2010). The resulting treatment-specific network models will be visualised using directed acyclic graphs (Shrier & Platt, 2008), which enable an intuitive interpretation of key mechanisms of change, their relative importance, and their interrelationships.

6. Ethical considerations

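### Section 5 names variables that the measures section does not list and that do not fit school pupils: staff role, WEMWBS, OLBI and mechanism questionnaires; hypothesis D names attitude where only activity level is measured

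*Protocol*

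**What the plan says.** **What is collected.** Protocol 4.3 gives the primary measure ("The PHQ-A is a nine-item questionnaire; each answered on a 0 to 3 Likert scale"), the GAD-A, demographics ("Participants will be asked to provide some demographic information, including age, gender, ethnicity") and one further item: "Questions related to the participants level of activity pre and post-intervention". Section 4.4 has participants complete these measures at baseline and a shortened version of the same questionnaire afterwards.

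**Who takes part.** Section 4.1 admits "Any child aged 11-17 (we will accept participants who turn 18 in the trial period) who may benefit", provided they attend a local school.

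**What is analysed.**
- Section 5.2 repeats the primary ANCOVA as a sensitivity analysis with a random intercept for site, and adds role "as a covariate (admin; mental health; other clinical role) and any other baseline demographics that may be unbalanced between groups". Section 5.3 carries the sensitivity analyses to every time-point for PHQ-A and GAD-A.
- Section 5.3 plans comparisons at weeks 6 and 36 "using the WEMWBS sub-domain scores".
- Section 5.4 sets PHQ-A as the dependent variable of a Bayesian network, then describes the target as post-treatment OLBI ("treatment OLBI). TAN produces a simple and parsimonious network model"). Its predictors are changes on mechanism questionnaires said to be on page 7.
- Hypothesis D in 3.3 states: "Attitude towards physical exercise will significantly improve following the intervention", with maintenance at 6 months. Section 3.2 makes attitude a secondary objective.

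**The concern.** An analysis plan can only use what the trial records. Here several named variables have no counterpart in the measures section, and one cannot apply to the participants at all.

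Three things are at stake. First, the sensitivity analysis is meant to show that the main finding is robust. With role removed, its remaining covariates are whichever demographics turn out to be unbalanced, so the adjustment set would be settled after the data are seen, in an open-label trial. Second, a secondary analysis and a stated hypothesis may reach the analysis stage without suitable data. A baseline score on WEMWBS or attitude cannot be recovered once the intervention has started. Third, an analyst who finds that the text does not work will have to improvise, and readers will not be able to tell planned choices from later ones.

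**Working it through.** No arithmetic applies. The check takes each variable named in 3.2, 3.3 and 5.2 to 5.4 and looks for it in 4.3 and in the data-collection text of 4.4.

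| Variable | Where it is used | What 4.3 and 4.4 provide | Result |
|---|---|---|---|
| Role (three staff categories) | 5.2, carried into 5.3 | Age, gender, ethnicity; participants are pupils | Cannot exist for this population |
| Site | 5.2, random intercept | Allocation is within regional area (4.4) | Can be run |
| Unbalanced demographics | 5.2 | Age, gender, ethnicity | Can be run, but chosen by observed imbalance |
| WEMWBS sub-domains | 5.3, weeks 6 and 36 | Not listed | No instrument |
| PHQ-A as network target | 5.4 | Listed | Available |
| OLBI as network target | 5.4, same paragraph | Not listed | Contradicts PHQ-A |
| Mechanism questionnaires | 5.4 | None listed | No listed mechanism predictors |
| Attitude towards exercise | 3.2, 3.3 (D) | Level of activity only | Construct mismatch |
| Knowledge | 5.3, exploratory | Not listed | No instrument |

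Four details matter for reading the table.

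1. *Could the measures be listed elsewhere?* The contents page puts 4.3 on page 6 and 4.4 on page 8, so the page 7 that 5.4 points to should fall within 4.3. That section contains no mechanism questionnaires. Section 4.4 adds no instrument: later surveys are a shorter form of the baseline one.

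2. *Could role be an unlisted demographic?* The demographics list is open-ended, since it gives examples. Even so, no extension of it could give a pupil an administrative or clinical staff role.

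3. *Is this a set of isolated slips?* Section 4.4 asks prize winners for a work address, and 6.2 points distressed participants to support for Trust employees. Together with role, these suggest text carried over from a study of staff. That is an inference, and the mismatches stand without it.

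4. *How is activity to be analysed?* The synopsis plans between- and within-group ANOVA of the physical activity measure at baseline and 6 weeks. Section 5.3 plans only an exploratory look at knowledge and activity levels before and after the intervention. The two disagree, and neither analyses attitude, so hypothesis D has no named analysis either.

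The primary analysis, an ANCOVA of PHQ-A between groups controlling for baseline severity, uses only listed variables.

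**The case against.** The strongest reply is that these are drafting leftovers away from the primary test, and that a separate SAP could settle the covariates. Part of that stands: the primary ANCOVA needs none of the missing variables, and a covariate list may be left to an SAP. But section 5 of the protocol is itself headed as the statistical analysis plan and names these variables. The point is what it states wrongly, not detail it omits.

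A reader might also infer more than the documents support:

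- *That the robustness check cannot be run at all.* Only the role term fails. The site random intercept and adjustment for collected demographics remain possible.
- *That OLBI blocks the network analysis.* PHQ-A is named as dependent variable in the same paragraph, so OLBI is a contradiction to remove. The unlisted mechanism questionnaires are the larger obstacle, and the analysis is exploratory.
- *That no attitude data will exist.* The survey is not shown, and 4.3 does not itemise its activity questions; some could touch on attitude. What can be said is that 4.3 names one construct and hypothesis D another.

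Figure 1 is not shown either, but its caption concerns design and measurement times, and 4.4 ties data collection to the measures already described.

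**Conclusion.** The point holds in limited form. Section 5 relies on variables that 4.3 does not list and, for role, that this population cannot have. As written:

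- one sensitivity covariate is impossible, and the others are picked by observed imbalance;
- one secondary analysis (WEMWBS) has no listed instrument;
- one exploratory analysis has two conflicting targets and no listed mechanism questionnaires;
- one of the four hypotheses (D), with its secondary objective, does not match the named measure, and the synopsis and 5.3 disagree on how activity is analysed.

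No bias or loss of power in the primary result follows. The conclusion assumes that 4.3 and 4.4 describe the surveys completely, apart from the open-ended demographics and the activity questions that are not itemised. The plan should be corrected before launch, but the primary comparison does not depend on it.

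**What to change.** 1. **Section 5.2.** Delete role. Replace the imbalance rule with a fixed list of collected baseline variables: age, gender and ethnicity. Keep the site random intercept. Recruitment route should not be substituted as if already available, because 4.3 does not list it.
2. **Section 5.3, WEMWBS.** Delete this analysis, or add the scale to 4.3 and to the baseline and later surveys before launch. Likewise remove knowledge or name its measure.
3. **Section 5.4.** Make PHQ-A the single target and limit the predictors to measures actually collected, or delete the section.
4. **Hypothesis D and the secondary objective.** Either add an attitude measure at all time-points before launch, including in the short surveys, or restate both as level of activity. In either case, test improvement with a week-6 between-group ANCOVA adjusted for baseline. A week-6 test cannot address maintenance, so add a comparison at 6-month follow-up; both groups will have had the intervention by then, so this is a within-participant comparison. Align the synopsis with 5.3.

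The cost is protocol wording. New data are needed only if the sponsor chooses to add WEMWBS, a knowledge measure or an attitude measure, which would lengthen the online surveys and must be in place before baseline.
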